6.2.4 Quality of Life in Alzheimer's Disease

The QOL-AD instrument is a brief, 13-item measure designed specifically to obtain a rating of the patient's QOL from both the patient and the caregiver (Logsdon et al. 1999; Logsdon et al. 2002). It was developed for individuals with dementia. It includes assessments of the individual's physical health, energy, mood, living situation, memory, family, marriage, friends, self as a whole, ability to do chores around the house, ability to do things for fun, money, and life as a whole. Caregivers complete the measure as a questionnaire about their patients' QOL, while patients complete it in interview format about their own QOL. Each item is rated on a 4-point scale. The score is the sum of all item ratings. Patient and caregiver reports can be evaluated separately and/or combined into a single score.

6.2.5 **Neuropsychiatric Inventory**

The NPI was developed to assess psychopathology in dementia patients (Cummings et al. 1994). The original NPI evaluated 10 neuropsychiatric disturbances common in dementia: delusions, hallucinations, agitation, dysphoria, anxiety, apathy, irritability, euphoria, disinhibition, and aberrant motor behavior. Two other domains, nighttime behavior disturbances and appetite and eating abnormalities, were subsequently added to the NPI (Cummings 1997). The score of each item (i.e., domain), if present, represents the product of symptom frequency (4-point scale) and severity (3-point scale). The NPI total score is the sum of the scores of the 10 neuropsychiatric domains (excluding nighttime behavior disturbances and appetite and eating abnormalities).

Additionally, a caregiver distress rating (or NPI-D, Kaufer et al. 1998) will be determined for the 12 individual domains (6-point scale), and the sum of the caregiver distress ratings for the

10 neuropsychiatric domains (excluding nighttime behavior disturbances and appetite and eating abnormalities) will be reported as the NPI Caregiver Distress total score.

The NPI will be used for subjects with an unpaid caregiver such as family or friend.

6.2.6 Neuropsychiatric Inventory – Nursing Home Version

The NPI-NH (Cummings et al. 1994; Wood et al. 2000) was developed to assess psychopathology in patients with dementia in nursing homes and evaluates 12 neuropsychiatric disturbances common in dementia: delusions, hallucinations, agitation, dysphoria, anxiety, apathy, irritability, euphoria, disinhibition, aberrant motor behavior, nighttime behavior disturbances, and appetite and eating abnormalities. The nursing home version of this scale was designed to examine psychopathology in nursing home patients and has been validated for use in this population (Wood et al. 2000). The score of each item (i.e., domain), if present, represents the product of symptom frequency (4-point scale) and severity (3-point scale). The NPI-NH total score is the sum of the scores of the 10 neuropsychiatric domains (excluding nighttime behavior disturbances and appetite and eating abnormalities).

Additionally, a caregiver occupational disruptiveness rating will be determined for the 12 individual domains (6-point scale), and the sum of the occupational disruptiveness ratings for the 10 neuropsychiatric domains (excluding nighttime behavior disturbances and appetite and eating abnormalities) will be reported as the NPI Occupational Disruptiveness total score.

The NPI-NH will be used for subjects with a paid caregiver.

6.2.7 **Neuropsychiatric Inventory Psychosis**

The NPI Psychosis score is the sum of domain A (delusions) and domain B (hallucinations) scores (each a product of symptom frequency and severity) of either the NPI or NPI-NH, as appropriate for a given subject.

6.2.8 **Neuropsychiatric Inventory – Clinician**

The NPI-C (de Medeiros et al. 2010) is a revised version of the NPI (Cummings et al. 1994) that includes expanded domains and items, and a clinician-rating methodology. With the NPI-C, data are acquired directly from patients, unlike the NPI where data are acquired only from informants.

There are two important rating changes in the NPI-C. The first is item-by-item scoring. In the NPI, a knowledgeable informant provides a global domain rating for frequency, severity, and level of caregiver distress related to the group of items within a given domain. The domain score is the product of the ratings for domain frequency and severity. In the NPI-C, ratings for frequency (0 [never] to 4 [very frequently]), severity (0 [none] to 3 [marked]) and distress (0 [not distressing to 5 [extremely distressing]) are provided for each item and summed to create a total domain score for each of these parameters.

In the clinician rating approach, the knowledgeable informant is first asked to provide frequency, severity, and distress ratings for items as described above. Separately, the rater also interviews the patient. Even if the patient lacks the ability or insight to describe experiences of neuropsychiatric symptoms accurately, the interview gives the clinician rater an opportunity to compare the knowledgeable informant's insights to the patient's perceptions.

To rate various item responses, the clinician can ask for additional details during either interview and may consult other sources of information such as the patient's chart or other caregivers familiar with the case in order to provide an overall severity rating for a given domain item.

The final NPI-C has 14 domains and a total of 142 items. The domains are delusions, hallucinations, agitation, aggression, dysphoria, anxiety, elation/euphoria, apathy/indifference, disinhibition, irritability/lability, aberrant motor disturbance, sleep disorders, appetite and eating disorders, and aberrant vocalizations.

Based upon informant ratings of individual symptom domain items including frequency, severity, and distress, along with frequency reported by patients, an overall clinical impression of severity is made by the rater for each domain symptom item and a total is provided based upon this severity score for each domain. For this study, only the domains of delusions (domain A) and hallucinations (domain B) will be assessed. The sum of the delusions and hallucinations clinical impression of severity is the NPI-C Psychosis score in this study.

The NPI-C assessment is incorporated into the study protocol as part of Amendment 3. However, it is acknowledged that the timing of availability of the NPI-C assessment may vary across different regions and clinical sites. Therefore, the administration of the NPI-C will commence when the necessary materials and resources become available/approved at each respective site. Until that time, the assessment is not required, but once available, sites should commence administration with subjects at their Screening visit. The NPI-C should not be first implemented with any subject at their Baseline visit or later.

6.3 **Safety Assessments**

6.3.1 **Physical and Neurological Examination**

A general physical examination will be conducted. The physical exam procedures will include the following organ systems:

- Head, ears, eyes, nose, and throat
- Skin
- Cardiovascular
- Respiratory
- Abdomen

- Genitourinary (optional)
- Musculoskeletal
- Lymph nodes

In addition, a neurological exam (cranial nerves, motor, sensory, reflexes, gait, and coordination) will be conducted.

6.3.2 Vital Signs

Vital signs will include body temperature, resting respiration rate, and orthostatic (supine and standing) blood pressure (BP, systolic and diastolic) and pulse rate.

The following procedures for orthostatic BP and pulse rate evaluation should be followed each time vital signs are measured. After the subject has been supine for approximately 5 minutes, BP and pulse rate will be measured and recorded, and the subject will then be instructed to rise to a standing position if able. Blood pressure and pulse rate will again be measured and recorded approximately 1 minute and 3 minutes (no later than 5 minutes) after standing. Subjects unable to stand may be assessed while sitting upright. The same position and arm should be used each time vital signs are measured for a given subject.

Orthostatic hypotension is defined as a decrease in systolic blood pressure \geq 20 mmHg or diastolic blood pressure \geq 10 mmHg after transitioning from the supine position to standing (or sitting upright if unable to stand) after 1 or 3 minutes.

6.3.3 Peripheral Edema

Table S–1. Peripheral edema present at Screening should be listed as medical history. New or worsening peripheral edema after Screening should be reported as an AE with stop/start dates noted, severity rated, relation to study drug, treatment, and outcome described, as for other types of AE. Clinicians should determine if any peripheral edema is pitting or non-pitting, arm or leg, unilateral or bilateral, acute or chronic, as well as its likely cause and treatment.

6.3.4 Height, Weight, and Body Mass Index

Height will be measured and reported.

Weight will be measured and reported.

Body mass index (BMI) will be calculated based on height at Screening and current weight measurements using the following formula: $Weight (kg)/[height (m)]^2$.

6.3.5 Electrocardiograms

All 12-lead ECGs will be complete, standardized recordings.

Electrocardiograms should be performed before blood sampling or at least 30 minutes after blood sampling. The subject should rest in a supine position for 5 minutes before the ECG is obtained. ECG tracings (paper or electronic) will be reviewed and interpreted by a qualified clinician at the research site. All ECGs will also be centrally read; the interpretation by the central cardiologist is considered the official interpretation. ECG tracings and results (ventricular rate, PR, QRS, QT, QTcF, and QTcB intervals) will be included and summarized in the subject's study records.

The ECG will be completed in triplicate at Screening and as a single tracing at all other visits. The following conditions apply:

- If the mean QTcF value from the set of ECGs done at Screening is prolonged due to an identifiable cause, and it is medically appropriate to address that cause, a repeat set of triplicate ECGs may be performed during Screening by agreement with the Medical Monitor. In this case, the repeat set of triplicate ECGs will be used in determination of subject eligibility.
- At Baseline, a subject may be enrolled based on the review and interpretation of ECG results by a qualified clinician at the research site. If the interpretation of the ECG by the central cardiologist indicates QTcF outside of the allowable range, the subject will be discontinued from the study, but enrollment of the subject will not be considered a protocol deviation.
- If a site performs in a single session more than the three ECGs prescribed at Screening or the single ECG prescribed at Baseline, the mean QTcF/QRS values of all the tracings of adequate quality will be used to determine eligibility.
- For all prescribed ECG assessments, repeats of ECGs performed because of abnormalities due to an identifiable cause are considered to be part of a separate ECG session. Repeat ECG values will not be averaged with values from another ECG session. All ECG values will be included in the subject's study records.

6.3.6 **Laboratory Evaluations**

Clinical laboratory sample collection is encouraged, but not required to be completed under fasting conditions. The laboratory evaluations will include, but are not limited to, the following:

Clinical chemistry serum tests (CHEM)

- Sodium, potassium, bicarbonate, chloride, phosphate, calcium, blood urea nitrogen (BUN), creatinine (CR), uric acid
 - o The eGFR will only be calculated from CR at Screening.
- Magnesium

- o Magnesium should only be performed at Screening.
- Glucose
- Albumin (ALB)
- Total protein
- ALT, AST, gamma-glutamyl transpeptidase (GGT), alkaline phosphatase (ALP), total bilirubin (TBIL), lactate dehydrogenase (LDH)
- Lipid panel
 - Total cholesterol, HDL cholesterol, triglycerides, LDL cholesterol, VLDL cholesterol, cholesterol/HDL ratio, non-HDL cholesterol
- HbA1c should only be performed at Screening and Visit 6 (EOT/ET).
- Creatine kinase (CK)/creatine phosphokinase (CPK)
- Vitamin B12
 - o Vitamin B12 should only be performed at Screening.

Endocrinology tests (ENDO)

- Thyroid function tests
 - o Thyroid-stimulating hormone (TSH) and free T4
 - TSH should be performed only at Screening.
 - Free T4 will be measured only if the TSH is abnormal.
- Prolactin

Hematology tests

- Complete blood count (CBC) including:
 - o White blood cell (WBC) count
 - o Complete differential (relative and absolute, including absolute neutrophil count)
 - o Hematocrit (Hct), hemoglobin, red blood cells (RBC), platelets
 - o Reticulocyte count

COVID-19 tests

• A COVID-19 test (PCR, rapid antigen, or transcription mediated amplification) will be performed at Screening.

Urinalysis (UA)

• Blood, RBCs, WBCs, protein, glucose, ketones, specific gravity, pH, nitrate/nitrite, leukocyte esterase, microscopic analysis.

Final Version: 2.0

• Reasonable efforts should be made to collect a urine sample from all subjects, and this is mandatory when the test is required for eligibility. After enrollment, where collection of a urine sample proves impractical or impossible (e.g., because the subject is incontinent), failure to collect a urine sample should be recorded in the subject's eCRF, and will not be considered a protocol deviation.

Urine toxicology screen

- Urine toxicology screen will test for controlled substances and alcohol (i.e., ethanol). The following controlled substances may be tested with a urine toxicology screen according to the schedule presented in Table 6–1: amphetamine, methamphetamine, barbiturates, cocaine, ecstasy (MDMA), phencyclidine (PCP), benzodiazepines, marijuana (THC), methadone, morphine/opiates. With certain exceptions described below, positive results will make a subject ineligible or result in ET.
- In the event of a positive result for a particular controlled substance or alcohol at any visit, a reflex test with the same sample will be performed to rule out a false positive. If this reflex test result for the same controlled substance or alcohol is negative, then the subject will not be ineligible or discontinued based on the prior positive result.
- The eligibility consequences of positive test results for amphetamines, barbiturates, alcohol, benzodiazepines, marijuana (THC), and opiates are described in Section 4.2.
- For continued participation in the study, positive test results for alcohol, benzodiazepines, marijuana (THC), or opiates will not necessarily result in ET. These will be evaluated by the Medical Monitor on a case-by-case basis. See Appendix F for prohibited benzodiazepines and opiates.
- Reasonable efforts should be made to collect a urine sample from all subjects; however, if after Screening collection of a urine sample proves impractical or impossible (e.g., because the subject is incontinent), controlled substances (including the opiate buprenorphine) and alcohol will be tested from a blood sample where local regulations permit this. Where testing from a blood sample cannot be performed, this will not be considered a protocol deviation for testing after enrollment. However, for eligibility, testing for controlled substances and alcohol in urine (not blood) must be performed.
- A urine toxicology screen should be performed as close as possible to the time of any seizure activity.

Blood alcohol test

 Blood alcohol test should be performed as close as possible to the time of any seizure activity.

Final Version: 2.0

Laboratory evaluations will be completed according to the schedule presented in Table 6–1 and procedures detailed in the study laboratory manual. Additional safety testing may be performed

Table 6–1 Safety Laboratory Evaluations

at the discretion of the Investigator or designee.

Visit	Tests	
Screening	CHEM, ENDO, CBC, COVID-19 test, UA, urine toxicology screen	
Visit 2 (Baseline)	CHEM, ENDO, CBC, UA, urine toxicology screen	
Visit 4 (Week 2)	CHEM, ENDO, CBC, UA	
Visit 6 (Week 6, EOT/ET)	CHEM, ENDO, CBC, UA, urine toxicology screen	

Abbreviations: CBC=complete blood count; CHEM=clinical chemistry serum tests; ENDO=endocrinology tests; COVID-19=coronavirus disease 2019; EOT=end of treatment; ET=early termination; UA=urinalysis

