- This Safety Follow-up Period includes two telephone calls (each to the subject and study partner/caregiver) for subjects who discontinue prematurely from the study, or who complete the treatment period of the study and do not rollover into the open-label extension study. These telephone calls will occur at 7 (±3) days and 30 (+4) days after the last dose of study drug, provided the subject or LAR has not withdrawn consent from further data collection.
- Vital signs will include body temperature, resting respiration rate, and orthostatic blood pressure (systolic and diastolic) and pulse rate. Blood pressure and pulse rate will be measured after the subject rests for 5 minutes in the supine position. The subject will then be asked to stand, and blood pressure and pulse

rate will be taken after standing for approximately 1 minute and then again after the subject has been standing for approximately 3 minutes (no later than 5 minutes). Subjects unable to stand may be assessed while sitting upright. The same position and arm should be used each time vital signs are measured for a given subject. Orthostatic hypotension is defined as a decrease in systolic blood pressure \geq 20 mmHg or diastolic blood pressure \geq 10 mmHg after transitioning from the supine position (after resting for 5 minutes) to standing after 1 or 3 minutes. If orthostatic hypotension is present, the Investigator should determine if the subject has associated symptoms such as postural dizziness or pre-syncope, as measured by UKU orthostatic dizziness severity greater than zero, or history of falls associated with orthostatic hypotension. If a subject with orthostatic hypotension at Screening or Baseline has associated symptoms, this will be exclusionary.

- The 12-lead ECG will be completed in triplicate at Screening. A single ECG will be completed at all other visits. The ECG should be completed before or at least 30 minutes after any blood sampling.
- Except for when required for eligibility, if collection of a urine sample for clinical laboratory tests (urinalysis) proves impractical or impossible, failure to collect a urine sample should be recorded in the subject's eCRF and will not be considered a protocol deviation.

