Limited, monitorable, and reversible cardiovascular system effects were seen in monkeys at supratherapeutic doses/exposures in nonclinical ACP-204 safety pharmacology single-dose (consisting of heart rate changes and PR, QRS, and QTc interval prolongations) and repeat-dose toxicity studies (PR and/or QRS interval prolongations). ACP-204 had no effect, at wide margins to the human therapeutic exposure, on the human ether-à-go-go-related potassium channel (HERG) in vitro, a key ion channel regulating cardiac action potential repolarization and the QT interval. Clinical results to date have not raised any concerns about QTc interval prolongation. To mitigate the risk of potential QTc prolongation, the present study has exclusion criteria to ensure that subjects at risk do not participate (Section 4.2).

Nonclinical data indicate that ACP-204 is primarily metabolized by cytochrome P450 3A4 enzyme (CYP3A4). Therefore, moderate and strong CYP3A4 inhibitors and inducers are prohibited or restricted medications in the present study (Appendix G).

Effects in animals associated with ACP-204 included dose and C_{max}-related convulsion-like activity observed in monkeys at supratherapeutic doses/exposures. Sustained convulsion-like activity was seen in a monkey after a 100 mg/kg dose, while in multiple repeat-dose toxicity studies, only one-time convulsion-like episodes were observed in two monkeys at a 40 mg/kg/day dose level. The events seen in repeat-dose studies were considered to occur at supratherapeutic exposure levels and were not considered adverse based on their very sporadic and transient occurrence, as animals recovered without treatment or intervention, and as affected animals had no further observable impact on their overall health and behavior, or notable postmortem central nervous system (CNS) findings.

Please refer to the current ACP-204 Investigator's brochure for additional nonclinical safety information.

1.5.2 **Known Potential Benefits**

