2.5 Pharmacokinetic and Pharmacokinetic/Pharmacodynamic Objectives

The PK and PK/pharmacodynamic (PD) objectives are:

- To characterize the PK of ACP-204 in subjects with ADP
- To assess the PK/PD relationship of ACP-204 using efficacy and safety endpoints in subjects with ADP

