6.3.13 Adverse Event Assessments

Adverse events will be assessed as per Table S-1 and Section 7.

6.4 **Pharmacokinetic Assessments**

As indicated in Table S-1, one PK sample will be collected at each of Weeks 0, 2, 4, and 6 from subjects in all parts of the study.

Pharmacokinetic samples will also be collected, if possible, immediately following any SAE or any AE leading to discontinuation.

For each individual subject, the PK samples collected at Weeks 2, 4, and 6 (i.e., postdose samples) should be collected at times that vary as much as possible between 2 and 24 hours after dosing within prespecified time intervals. One sample should be collected 2 to 5 hours after dosing, one sample should be collected 5 to 8 hours after dosing, and one sample should be collected 8 to 24 hours after dosing. If this is not possible and samples at two different visits must be collected within the same time interval after dosing, then these should vary within the interval to provide as much variation as possible overall. PK sample collection times will depend on both dose timing and clinic visit timing. Because subjects may take their dose at home or in clinic on these visit days, and sites may schedule the times of these visits to target desired PK sample collection times, PK sample collection should not require excessively long stays at the clinic.

For all post-baseline PK samples (scheduled and unscheduled), the dates and times of administration of the last three doses of study drug should be recorded, as well as the date and time of the sample draw. The baseline PK sample will be taken predose.

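### On-treatment ECGs have no set time after dose, no maximum gap to the PK draw and no required clock time, so they may cluster at trough exposure

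*Protocol*

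**What the plan says.** **ECG timing.** Section 6.3.5 states "Electrocardiograms should be performed before blood sampling or at least 30 minutes after blood sampling". The Table S-1 footnote repeats this for all draws: "The ECG should be completed before or at least 30 minutes after any blood sampling". Screening uses triplicate tracings; after that, "A single ECG will be completed at all other visits". Table S-1 schedules on-treatment ECGs at Weeks 1, 2, 4 and 6.

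**PK timing.** Section 6.4 is much more specific. It says that "one PK sample will be collected at each of Weeks 0, 2, 4, and 6 from" subjects in all parts, the Week 0 sample being predose. For Weeks 2, 4 and 6, "One sample should be collected 2 to 5 hours after dosing, one sample should be collected 5 to 8 hours after dosing", and the third at 8 to 24 hours. Two visits may share a window if the plan cannot be met. The times of the last three doses and of the draw are recorded. The section continues "Because subjects may take their dose at home or in clinic on these visit days", and because visit times can be chosen to suit the targets, it does not expect very long clinic stays.

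**Use of the data.** Section 2.5 has the objective "To assess the PK/PD relationship of ACP-204 using efficacy and safety endpoints in subjects with ADP". Section 9.8.2 plans descriptive ECG statistics by visit and categorical QTc analyses based on the E14 guidance. Section 9.9 plans exposure-response modelling of relevant safety endpoints under a separate analysis plan. Section 1.5.1 reports "PR, QRS, and QTc interval prolongations" in monkeys at supratherapeutic exposures.

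**The concern.** The protocol spreads the PK samples over the dosing interval but leaves the ECG, the measurement to be related to exposure, free to fall anywhere in it. A site that records the ECG on arrival, gives the dose in clinic and draws PK a few hours later follows every rule. Its ECG then reflects roughly 24 h after the previous dose, while its concentration reflects the new dose.

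Two things are at stake. First, QTc tables by visit and by category describe whatever exposure was present at the ECG. If that is mostly trough, they say little about peak, and a reader cannot tell at which visits this happened. This needs no concentration-QTc model. Second, an exposure-response analysis that pairs the ECG with the same-visit measured concentration would use a mismatched exposure.

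**Working it through.** The protocol gives no figure on this point, so there is none to reproduce.

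**Inputs from the protocol**
- Half-life about 20 h, once-daily dosing, linear PK (Section 1.4.2), so ke = ln 2 / 20 = 0.0347 per hour and tau = 24 h.
- PK windows 2-5, 5-8 and 8-24 h (Section 6.4).
- Four on-treatment ECGs and three scheduled on-treatment PK samples (Table S-1). At most 3 of the 4 ECGs have a scheduled concentration, because Week 1 has none.

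**Assumptions (not in the protocol)**
- Single-dose Tmax of 2 to 8 h for the concentration ratios, 2 to 6 h for the slopes.
- Between-subject CV of exposure 20% to 40%; the protocol says only that variability is low to moderate.
- QTc effect linear in concentration, with no delay.

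**Step 1: trough against peak.** Decay alone from 2 h to 24 h is 2^(22/20) = 2.14-fold. With absorption, the one-compartment steady-state profile is

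C(t) ∝ ka/(ka − ke) × [e^(−ke·t)/(1 − e^(−ke·tau)) − e^(−ka·t)/(1 − e^(−ka·tau))],

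with ka solved from Tmax = ln(ka/ke)/(ka − ke).

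| Assumed Tmax | ka (per h) | Peak/trough | Mean/trough, 2-5 h | 5-8 h | 8-24 h |
|---|---|---|---|---|---|
| 2 h | 2.083 | 2.13 | 2.03 | 1.83 | 1.34 |
| 4 h | 0.828 | 1.96 | 1.94 | 1.83 | 1.34 |
| 6 h | 0.469 | 1.81 | 1.76 | 1.77 | 1.33 |
| 8 h | 0.308 | 1.66 | 1.58 | 1.65 | 1.32 |

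A predose ECG therefore sees 1/2.13 = 0.47 to 1/1.66 = 0.60 of the peak concentration. Under the linear assumption it shows the same share of the peak QTc effect.

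**Step 2: naive pairing.** Subjects were simulated on 0, 30 or 60 mg with three visits each. The QTc effect at the ECG time was regressed on the concentration at the PK time; the true slope is 1.

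| ECG and PK timing | Fitted slope / true slope |
|---|---|
| ECG 0.5 h before the draw, PK in the three windows | 1.00-1.02 |
| ECG 1 h after the draw, PK in the three windows | 0.97-0.99 |
| Only the 2-5 h visit has a trough ECG; other ECGs 1 h before the draw | 0.76-0.83 |
| All ECGs at trough, PK in the three windows | 0.53-0.59 |
| All ECGs at trough, all PK at 2-5 h (outside the planned windows) | 0.49-0.57 |
| ECG at 4 h, all PK at 8-24 h (outside the planned windows) | 1.28-1.42 |

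The worst-case row depends on the model. Placing the variability on clearance (CV 20-35%, ka 0.3-1.0 per hour) gives 0.58-0.72 for all ECGs at trough with PK in the three windows.

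**The case against.** The other side has several good points.

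- **Visits are likely to be short.** Section 6.4 lets subjects dose at home and lets sites choose visit times. With home dosing and a timed visit, an arrival ECG is already postdose and close to the draw. The all-trough case needs clinic dosing followed by waits of at least 5 h and at least 8 h for two of the samples, which the section does not expect. This stands: that case is unlikely, and a mispaired 2-5 h visit is the plausible one.
- **No concentration-QTc regression is named.** The slope figures apply only to naive same-visit pairing. Population PK is planned and dose times are recorded at PK visits, so concentration at the ECG time could be predicted. This stands if the ECG time is known, which the protocol does not require. Tracings may carry a time stamp, but the protocol does not say that it is captured. Prediction cannot create near-peak ECGs that were never taken.
- **The cardiac signal is limited.** Section 1.5.1 also reports no HERG effect at wide margins and no clinical QTc concern to date. This lowers the urgency but does not remove the stated safety objective.
- **Tmax is not given.** Near-peak cannot be placed in a particular window, which is why ranges are shown.

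A reader might infer that every on-treatment ECG can be paired with a near-peak concentration, and that the concentration-QTc relation is therefore understated. The documents do not support this. Week 1 has no PK sample, the later samples are to be spread out to 24 h, and the same rule permits an ECG nearer peak than its sample, which overstates the slope. Nor is the ECG wholly unlinked from the PK draw: the ordering rule covers any blood sampling. What is missing is an upper limit on the gap.

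**Conclusion.** The gap is real and modest. The protocol orders the ECG relative to blood draws but fixes no time after dose, no maximum interval to the PK sample and no recorded ECG time, so on-treatment ECGs may cluster at trough.

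The main consequence falls on the QTc summaries actually planned: at a visit with a predose ECG they reflect about 47% to 60% of peak concentration, under the assumed absorption. The consequence for exposure-response work is conditional. Naive pairing could give about 0.76 to 0.83 of the true slope in the plausible case, about 0.5 to 0.6 in an unlikely worst case (milder under other variability assumptions), or more than 1 if the mismatch runs the other way. How often sites would record predose ECGs is unknown, so the net effect cannot be estimated from the protocol. The point is a cheap improvement to safety data, and the efficacy analyses are not affected.

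**What to change.** In Section 6.3.5 and the Table S-1 ECG footnote:

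1. Require the Week 2, 4 and 6 ECG to be recorded within about 30 minutes before that visit's PK draw. This meets the existing before-sampling rule.
2. State that any other blood draw at the visit (Table S-1 has safety laboratory tests at Weeks 2 and 6) is taken with the PK draw or at least 30 minutes before the ECG.
3. Record the ECG clock time at every on-treatment visit. At Week 1, which has no PK sample, also record the time of the last dose.

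In the simulation, an ECG 0.5 h before the draw returns a slope of 1.00 to 1.02 of the truth. The ECGs will spread over the dosing interval only as far as the PK windows are met, since Section 6.4 allows two visits to share a window.

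No extra ECG, blood draw or staff is needed. The cost is a revised footnote and sentence, time fields where they are not already captured, and slightly less freedom in sequencing the visit.
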